Maslovitz et al. (31) reported the rate of vaginal bleeding of 1.8% following transcervical Foley catheter insertion. However, the bleeding was minor with unaltered haemoglobin levels and coagulation profile. There was also no case of cervical tear which might result in postpartum haemorrhage. Besides, risk of change of fetal vertex presentation to breech was reported to be 1.3% (31). This was probably related to concomitant presence of unengaged free-floating fetus and contraction following Foley catheter insertion which resulted in flipping movement of the fetus. Risk of poor APGAR and NICU admission was not significantly higher compared to other IOL methods eg. prostaglandin and oxytocin (24, 26).

Till date, there is paucity of evidence on the superiority of membrane sweeping and transcervical Foley catheter in IOL in previous Caesarean delivery. Both methods have the same mechanism action by increasing local production of endogenous prostaglandin (1). The aim of this study is to evaluate the effectiveness of membrane sweeping and transcervical Foley catheter insertion for IOL in women with previous Caesarean delivery.

OBJECTIVES AND PURPOSE

1. General objective:
 - a. To compare the effectiveness of membrane sweeping and transcervical Foley catheter for IOL in women with one previous Caesarean delivery.

2. Specific objectives:

- a. To compare the following induction outcomes between membrane sweeping and transcervical Foley catheter for IOL in women with one previous Caesarean delivery.
 - i. Improvement of modified Bishop score at interval of 24 hours and 48 hours, respectively.
 - ii. The requirement of oxytocin following IOL.
- b. To compare the following delivery outcomes between membrane sweeping and transcervical Foley catheter for IOL in women with one previous Caesarean delivery.
 - i. Mode of delivery.
 - ii. Overall:
 - Induction to delivery interval.
 - Oxytocin augmentation duration.
 - iii. Vaginal delivery subgroup:
 - Induction to delivery interval.
 - Amniotomy to delivery interval.
 - Duration of oxytocin augmentation.
 - Vaginal delivery rate within 24 hours of induction.
 - Vaginal delivery rate between 24-48 hours of induction.
- c. To compare the maternal outcomes between membrane sweeping and transcervical Foley catheter for IOL in women with one previous Caesarean delivery.
 - i. Uterine hyperstimulation.
 - ii. Uterine rupture.
 - iii. Post-partum haemorrhage.
 - iv. Maternal pyrexia.
 - v. Duration of hospitalization.

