 - c. Informed consent available in either English or Malay language (See Appendix 2) will be obtained prior to enrollment into the study. The consent will be taken by the principal investigator at time of admission in Sibug Hospital Labour Ward.
 - d. A data collection form will be filled up and details including personal information will be obtained (Appendix 3).
 - e. Eligible subjects will be randomly assigned to one of the treatment groups below.
 - i. Group 1: IOL with membranes sweeping
 - ii. Group 2: IOL with transcervical Foley catheter
 - f. Blocked randomisation, in a block size of 6 and an allocation ratio of 1:1, will be performed using a computer-generated randomisation sequence by Research Randomizer (available online at <https://www.randomizer.org/>). The allocation assignment indicating “membrane sweeping” or “transcervical Foley catheter” will be sealed in sequentially numbered, opaque envelopes by principal investigator, . Envelopes will be kept in a locked box in Labour Ward. When study consent is signed, the next sequential envelope will be taken out from the box and opened to determine allocation.

- g. This is a non-blinded study in which subjects, medical staffs, and investigators are not blinded to group assignment. This is because both IOL methods are distinctly different procedure. However, both intervention arms are considered receiving equal treatment. In term of safety, both membrane sweeping and transcervical Foley catheter are non-pharmacological in nature and thus the risk of scar rupture does not differ in both methods. In term of efficacy, there is no previous study to compare effectiveness between these two methods. Individual studies revealed that membrane sweeping is likely to reduce the need for formal IOL in post-date pregnancy and transcervical Foley catheter could improve cervical favourability.
- h. IOL will be done on the next morning. Pre-induction cardiotocograph (CTG) will be performed to ensure normal fetal heart rate prior to IOL.
- i. In Group 1, membrane sweeping involves the insertion of a digit past the internal cervical os followed by three circumferential passes of the digit causing separation of the membranes from the lower uterine segment. When the cervix is closed, a massage of the cervical surface for 15 to 30 seconds will be performed instead. Membrane sweeping will be undertaken twice a day at 8 to 10 hours apart.

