- j. In Group 2, transcervical Foley catheter No. 18 F will be inserted under aseptic technique into the endocervical canal surpassed beyond the internal os. The balloon will be inflated with 60 ml of sterile water and the catheter is plastered to patient's thigh with gentle traction. The catheter will be checked for its position and the traction at 6 hours interval. If it were expelled spontaneously, it would not be re-inserted. Otherwise, the catheter will be removed after 24 hours.
- k. Post-induction CTG will be performed at 1 hour after the first membrane sweeping in Group 1 and after transcervical Foley catheter insertion in Group 2.
- l. The uterine contractions, maternal temperature and fetal heart rate (via handheld Doppler device) will be monitored every 4 hours.
- m. After 24 hours, improvement of modified Bishop score will be assessed.
 - i. If the cervix is favourable for amniotomy, amniotomy will be performed followed by augmentation with intravenous oxytocin.

- ii. If the cervix is still unfavourable and amniotomy is impossible, membrane sweeping will be continued for one more day in Group 1 whereas conservative management will be undertaken for one day in Group 2. Suitability for amniotomy will be reassessed on the next day.
 - n. After amniotomy, subsequent intrapartum management will be based on the hospital protocol.
 - o. Oxytocin augmentation will be started when desired contractions are not achieved at 2 hours after amniotomy or labour progress falls below the action line of partogram.
 - p. Our oxytocin infusion regime begins with 2 mU/min. An increment in dosage is made every 30 minutes until desired contractions of 3-4 in 10 minutes lasting 45-60 seconds. The maximum oxytocin dose is 16 mU/min.
 - q. Continuous CTG monitoring will be undertaken throughout the labour process.
 - r. Oxytocin augmentation will not be started or will be withheld when there is non-reassuring fetal heart rate.
 - s. If amniotomy is still impossible after 2 days of IOL, the ward Obstetrician will discuss with women regarding option of Caesarean section.
6. Criteria for suspending or terminating the study:

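### Step 5.m.i, read literally, gives oxytocin to every woman who has amniotomy, which contradicts the indication rule in step 5.o

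*Combined protocol and SAP*

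**What the plan says.** Step m of the study procedure (Trial Design, item 5) sets the assessment at 24 hours. Under m.i, if the cervix is favourable, "amniotomy will be performed followed by augmentation with intravenous oxytocin". The only condition in that sentence is on the amniotomy.

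Step o gives a start rule for the same drug: "Oxytocin augmentation will be started when desired contractions are not achieved at 2 hours after amniotomy or labour progress falls below the action line" of the partogram.

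The surrounding steps do not say which of the two prevails:

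- Step n: "After amniotomy, subsequent intrapartum management will be based on the hospital protocol".
- Step p sets the dose, starting at 2 mU/min and rising every 30 minutes: "The maximum oxytocin dose is 16 mU/min".
- Step r is a safety hold: "Oxytocin augmentation will not be started or will be withheld when there is non-reassuring fetal heart rate".

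Elsewhere, oxytocin is treated as something a woman may or may not need. Treatment and Procedures, item 1.b, permits it where contractions fall short. Objective 2.a.ii is "The requirement of oxytocin following IOL". Assessment of Efficacy, 2.a.ii, makes that need a secondary outcome, Statistics 3.a gives it a chi-square test, and Section C of the data collection form records it as yes or no.

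**The concern.** The two steps disagree on whether a woman who contracts well after amniotomy receives oxytocin at all, as well as on when it starts. Two things are at stake.

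**Exposure.** Every participant has a uterine scar, and the introduction names scar rupture as the main worry with induction in this population. Followed literally, m.i gives oxytocin to women who have no indication for it under step o. Dose titration, the cap, continuous CTG and the hold in step r limit the risk but do not remove the unneeded exposure.

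**A tested secondary outcome.** Need for oxytocin is informative only if oxytocin is given according to need. If it follows automatically from amniotomy, the outcome becomes close to a count of amniotomies. Duration of oxytocin, also a secondary outcome, depends on the start rule too.

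Staff are not blinded (step g), so nothing in the design prevents the two wordings from being applied differently by different clinicians.

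**Working it through.** The plan states no figure on this point, so the check sets the texts side by side.

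**1. What each step implies for a woman who has had amniotomy at the 24-hour assessment**

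| Situation after amniotomy | Step m.i read literally | Step o |
|---|---|---|
| Adequate contractions, progress never below the action line | Oxytocin | No oxytocin |
| Inadequate contractions at 2 hours | Oxytocin, no wait stated | Oxytocin at 2 hours |
| Adequate contractions, progress later below the action line | Oxytocin, no wait stated | Oxytocin when the line is crossed |
| Fetal heart rate of concern | Not started or stopped (step r) | Not started or stopped (step r) |

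The first row is the contradiction. The second and third differ in timing only. The fourth shows that step r applies equally under both readings, so it cannot decide between them.

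**2. Which rule was meant**

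- Step o's 2-hour trigger would have little function if oxytocin were already running.
- Item 1.b of Treatment and Procedures carries a condition in line with step o.
- The objective, outcome and form item all presuppose that some women will not need oxytocin.
- Where the cervix is unfavourable at 24 hours, m.ii says "Suitability for amniotomy will be reassessed on the next day" and does not mention oxytocin. Steps n and o are tied to amniotomy without any limit on the day, so they cover the later amniotomy.

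All four point to step o as the general rule and to m.i as the faulty sentence.

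**3. What literal use of m.i does to the oxytocin outcome**

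Let *a* be the share of an arm having amniotomy under m.i, and *q* the share of those women who would ever meet a trigger in step o. Ignore holds under step r and women who labour outside this pathway.

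- Share given oxytocin under literal m.i: *a*
- Share given oxytocin under step o: *a* × *q*
- Given oxytocin under m.i but not under o: *a* − *a* × *q* = *a*(1 − *q*)
- Difference between arms (Foley F minus sweeping S) under m.i: *a*F − *a*S
- Same difference under step o: *a*F × *q*F − *a*S × *q*S

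The difference under m.i does not contain *q*, so it says nothing about need. It can depart from zero simply because more women in one arm reach amniotomy. The plan itself raises that possibility in step g: "transcervical Foley catheter could improve cervical favourability". The documents give neither *a* nor *q* for either arm, so no numerical size follows.

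**4. Timing**

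For women who meet step o's contraction trigger, m.i started at once would bring oxytocin forward by up to 2 hours (2 × 60 = 120 minutes). This limit does not extend to the action-line trigger, which has no fixed time.

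**The case against.** The strongest reply is that the steps reconcile on an ordinary reading. Step m.i gives the order of events, and steps n to r then supply the detail: when to start, at what dose, and when to hold. Since m.i names no start time, step o fills a gap. Labour ward staff who know their own protocol would probably not give oxytocin to a woman who is contracting well. The flow chart and the hospital protocol cited in step n cannot be seen here, and either may remove any doubt.

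Much of this stands. It supports step o as the intended rule and keeps the point minor, and nothing unseen is counted against the plan. It does not rescue the sentence in m.i, which says that augmentation follows amniotomy and carries no reference to step o. Even if the flow chart is clear, a procedural sentence that contradicts it should be corrected.

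Two stronger readings are tempting and are not supported:

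- A reader might infer that the plan has no oxytocin rule for amniotomy on the second day. Steps n and o apply after any amniotomy, so it does.
- A reader might infer that the data form is deficient because it omits the indication and start time for oxytocin. Use and duration are both recorded, which is what the stated outcomes need, and the hospital keeps the medical records.

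**Conclusion.** The point holds as a minor one: m.i is wrong as written. It contradicts step o for women who contract adequately and progress normally after amniotomy. The consequences arise only if staff follow m.i literally, which is the less likely reading.

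The size cannot be derived from the documents. A reader might be drawn to attach a count. For example, assuming 60–80% of women have amniotomy and 40–70% of those would meet a step-o trigger, *a*(1 − *q*) runs from 0.60 × 0.30 = 0.18 to 0.80 × 0.60 = 0.48, or 18 to 48 women per 100. Those shares are pure assumption, and the range also supposes that everyone follows m.i, so it shows the mechanism and is not an estimate.

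Nor do the documents support a claim of bias toward one arm, since m.i is worded identically for both. The definition of the primary outcome, the overall induction to delivery interval, does not depend on which rule is used.

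**What to change.** Reword the end of m.i to read: *amniotomy will be performed, followed by intravenous oxytocin if indicated under step o*. Apply it identically in both arms, and check that the Appendix 1 flow chart says the same.

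The cost is one phrase and one consistency check. The outcome definitions, the analysis and the data form stay as they are.

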 - a. Transcervical Foley catheter is found to have unreasonable and significant risks to subjects. The risks include uterine rupture, maternal sepsis, severe cervical trauma, and neonatal sepsis. However, all these serious adverse outcomes were infrequent risk based on literature review. Literature review showed that the risk of uterine rupture in Foley catheter arm is comparable to women with scarred uterus undergoing spontaneous labour (18, 25). There is small risk of maternal pyrexia or infection but no case of maternal or neonatal sepsis was reported (8, 28-30). Similarly, no case of cervical trauma was reported as well (31).
7. Study instruments:
 - a. Data collection form which consists of:
 - i. SECTION A: Subjects' demographic information (gravida, parity, gestational age, maternal height and weight, body mass index, details of previous Caesarean delivery, indication of IOL).

- ii. SECTION B: Subjects' induction outcomes (serial changes in modified Bishop score).
 - iii. SECTION C: Subjects' delivery outcomes (oxytocin requirement, mode of delivery, induction to delivery interval, overall duration of oxytocin augmentation, intrapartum details for the vaginal delivery (including instrumental delivery) subgroup, estimated blood loss, maternal and neonatal outcomes.
 - iv. SECTION D: 'Subjects' satisfaction on the care they received.
- b. Membrane sweeping:
- i. An IOL method involving the insertion of a digit past the internal cervical os followed by three circumferential passes of the digit causing separation of the membranes from the lower uterine segment.
 - ii. When the cervix is closed, a massage of the cervical surface for 15 to 30 seconds will be performed instead.
- c. Transcervical Foley catheter:
- i. An IOL method involving insertion of a balloon catheter under aseptic technique into the endocervical canal surpassed beyond the internal os.
 - ii. The balloon will be inflated with 60 ml of sterile water and the catheter is plastered to patient's thigh with gentle traction.
 - iii. Foley catheter is an indwelling catheter made of latex rubber.
- d. Modified Bishop score: (see Figure 1)
- i. A group of measurements made at internal examination, used to determine whether the cervix is favourable or not.
 - ii. The score is based on the station, dilation, effacement (or length), position and consistency of the cervix.
 - iii. A score of 8 or more generally indicates that the cervix is ripe (2).

Figure 1: modified Bishop score

Score	0	1	2	3

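### The only criterion for suspending the study (Trial Design 6.a) covers Foley catheter risks alone, so uterine ruptures or other serious events in the sweeping arm cannot meet it, although the protocol holds scar-rupture risk equal between methods

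*Combined protocol and SAP*

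**What the plan says.** In the combined protocol and SAP, Trial Design item 6 contains a single criterion, 6.a: "Transcervical Foley catheter is found to have unreasonable and significant risks to subjects". It continues: "The risks include uterine rupture, maternal sepsis, severe cervical trauma, and neonatal sepsis". The rest of 6.a reviews literature on the catheter, including the remark that "There is small risk of maternal pyrexia or infection". Item 7 then moves on to study instruments.

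Elsewhere the protocol says the following.

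- **Trial Design 5.g**, on safety: "the risk of scar rupture does not differ in both methods". Treatment and Procedures 2 and Assessment of Safety 1 liken the rupture risk of both methods to that of spontaneous labour.
- **Trial Design 5.i and 5.m.ii**, on the sweeping schedule: "Membrane sweeping will be undertaken twice a day at 8 to 10 hours apart", and, if the cervix is still unfavourable after 24 hours, "membrane sweeping will be continued for one more day in Group 1".
- **Trial Design 5.m.i**, for both groups once the cervix is favourable: "amniotomy will be performed followed by augmentation with intravenous oxytocin". The oxytocin rules in 5.o to 5.r do not distinguish between groups.
- **Assessment of Safety 3 and 4**: adverse events of any type are reported, with set timelines and follow-up. Nothing there links a report to suspension of the study.
- **Selection and Withdrawal of Subjects 4.b**: the interim analysis after 24 women has the calculation of the final sample size as its stated purpose.

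**The concern.** A suspension criterion tells investigators when to stop randomising and look again. Here it is worded so that only one arm can set it off. That sits badly with a protocol that holds scar-rupture risk equal between the arms and lists rupture first among the risks that would justify stopping.

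If ruptures or sepsis occurred in women allocated to sweeping, staff would report and treat them, but the written rule would give no ground to pause recruitment. There would be no stated trigger to review the trial's sweeping schedule or the labour management that follows it. The background calls scar rupture the greatest concern in these women and notes that the hospital has few consultants to cope with it, so the rule ought to cover every randomised woman.

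**Working it through.** There is no numerical boundary in 6.a to reproduce. The check is a comparison of texts.

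1. **Scope of the criterion.** Item 6 has one entry, and its grammatical subject is the Foley catheter. A rupture in a woman who received sweeping is not a risk of the catheter, so it cannot satisfy 6.a. At most, sweeping-arm events serve as the comparison when the catheter's risk is judged. In that role, more ruptures after sweeping would make the catheter look better, not bring the rule into play.

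2. **The protocol's premise on rupture.** 5.g says the risk does not differ. If so, a rupture carries the same weight whichever arm it falls in. Under 6.a it counts in one arm only.

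3. **Events after induction.** Amniotomy and the oxytocin regimen follow the same rules in both groups. A hazard arising at that stage in a sweeping woman is also outside 6.a. This does not assume equal oxytocin exposure, because oxytocin requirement and duration are outcomes of the trial.

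4. **Other routes.** Safety 3 sends reports to an external platform but does not say what may follow from them. Safety 4.b withdraws an individual woman after a vasovagal attack, which is a step for one subject and not for the trial. The interim analysis has no stated safety role. No monitoring committee is described. The Appendix 1 flow chart is not shown and could not be checked.

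5. **Scale, for orientation only.** Allocation is "in a block size of 6 and an allocation ratio of 1:1". The share of expected ruptures falling in the sweeping arm is p_sweep / (p_sweep + p_Foley).
   - With equal risk, as in 5.g: p / (p + p) = 0.50.
   - If the background's statement that no rupture was reported after sweeping in scarred uteri holds in this trial: 0 / (0 + p_Foley) = 0.
   - The absolute number is small. Assume for sweeping the lowest and highest relevant rates quoted in the background, 0.52% (spontaneous labour) and 1.6% (Foley, retrospective cohort). Expected ruptures among the first 12 sweeping women are then 12 × 0.0052 = 0.06 to 12 × 0.016 = 0.19.
   - The final sample size is not given, so no figure for the full trial is offered.

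The share runs from none to half, depending on which statement in the protocol is believed. The point therefore rests on steps 1, 2 and 4, not on step 5.

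**The case against.** The strongest defence is that sweeping is routinely offered at this hospital to women with a previous Caesarean, so the catheter is the method being tested against usual care. Aiming the criterion at the newer method is a recognisable choice, and halting the trial would not take sweeping away from women who are offered it anyway. This may well explain the wording. But the protocol does not give it as the reason. It also does not show whether routine sweeping follows the trial's twice-daily schedule of up to two days; the text is silent either way. Suspension also stops randomisation and prompts review, which has a purpose even when the triggering arm is close to usual care.

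Second, the statement of equal risk covers rupture only. For infection the background separates the methods: the catheter may in theory raise the risk, with conflicting data, whereas sweeping did not increase it. A reader might infer from Safety 3.c and 3.d, which attach no method to cervical tear, rupture or maternal sepsis, that the protocol treats all of these as equally likely in both arms. It does not. Those are examples given for reporting timelines. This part of the defence stands, and the inconsistency is confined to rupture. The gap in 6.a still applies to any serious event in the sweeping arm.

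Third, Safety 2 describes amniotomy and other labour procedures as standard care, and 5.n places management after amniotomy under the hospital protocol. Safety 2 does not name oxytocin, but read together these passages describe usual practice, and suspending the trial would not by itself change it. That weakens any argument from the shared regimen. It does not explain why the same event should count in one arm and not in the other.

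Finally, authorities who receive the reports might intervene. They might, but the documents do not describe it, and item 6 is where the criteria are meant to be stated.

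**Conclusion.** The point holds as a one-sided safety rule. The only stated criterion for suspending or terminating the study can be met by catheter risks alone, although the protocol states that rupture risk is the same for both methods and lists rupture first. This rests on the wording of 6.a and 5.g and on the absence of any other route in the visible text. It does not depend on a rupture rate or on the final sample size.

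It is a minor patient-safety improvement. Three stronger readings are tempting, and the documents do not support them.

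- **Harm in the sweeping arm would go unnoticed or untreated.** Safety 3 and 4 require reporting and follow-up of adverse events without limiting this to one arm.
- **The study could not in practice be stopped for sweeping-arm events.** The documents do not say what the bodies receiving the reports may do, so this cannot be concluded.
- **The trial's result is affected.** Nothing in the wording of 6.a bears on the induction-to-delivery interval or its analysis.

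**What to change.** Reword 6.a so that it covers every randomised woman, for example: *Either induction method, or the labour management that follows it in the trial, is judged to carry unreasonable and significant risk (for example neonatal or maternal sepsis, uterine rupture or severe cervical trauma). Recruitment will then be suspended and the events reviewed.*

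This is an amendment of wording only, with no new data, visits or staff. The small downside is that events in the routine-care arm can also prompt suspension and review. The rewording does not set a threshold or name who decides. Stating both would make the rule easier to apply, but the correction of scope does not depend on it.

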Dilatation (cm)	1	1-2	3-4	>4
Length of cervix (cm)	>4	2-4	1-2	<1
Station	-3	-2	-1	0
Consistency	Firm	Average	Soft	-

Position	Posterior	Mid/Anterior	-	-
----------	-----------	--------------	---	---

SELECTION AND WITHDRAWAL OF SUBJECTS

1. Sample population:
 - a. All pregnant women with one previous Caesarean section who are admitted to Sibug Hospital for IOL will be recruited in the study.
2. Inclusion criteria:
 - a. The inclusion criteria are age at least 18 years old, gestational age ≥ 37 weeks, singleton pregnancy, reassuring fetal status and modified Bishop score ≤ 6 .
3. Exclusion criteria:
 - a. Women with ruptured membranes, intrauterine death, polyhydramnios, severe fetal anomalies, multiple pregnancy.
 - b. Women with contraindications for IOL eg. placenta previa, suspected macrosomia, suspected cephalopelvic disproportion, non-cephalic presentation, and obstructive pelvic masses.
4. Sample size determination:
 - a. We had searched electronic databases including PubMed, Cochrane Library, Scopus, Ovid, JSTOR and Google Scholar. We found that there was no study comparing the two IOL methods, thus no prior information is available for sample size calculation.
 - b. Based on Julious SA (32), we will recruit 24 subjects (a sample size of 12 per group) first, then do an interim analysis and calculate the actual sample size required for a full RCT. The justifications for this interim sample size are based on rationale about feasibility, precision about the mean and variance, and regulatory considerations.
 - c. With α at 0.05 and power at 0.8, the final sample size will be calculated based on the study primary outcome of induction to delivery interval. As this outcome is a continuous data, we will use the following formula by Snedecor and Cochran 1989 to calculate the sample size (including 15% of dropout rate).

$$n = 1 + 2C \left(\frac{s}{d} \right)^2$$

s = standard deviation,

d = the difference to be detected, and

C = constant

5. Consent taking:

- a. Pregnant women with one previous Caesarean section who are indicated for IOL and eligible will be recruited in the study.
- b. Participation of the subjects is voluntary and will not affect medical services.
- c. Informed consent available in either English or Malay language (See Appendix 2) will be obtained prior to enrollment into the study.
- d. The consent will be taken by the principal investigator at time of admission in Sibu Hospital Labour Ward.

6. Subject withdrawal:

- a. Criteria:

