 - x. Duration of hospitalisation.
- d. Neonatal outcomes:
 - i. APGAR score at 5 minutes.
 - ii. Cord pH.

ASSESSMENT OF SAFETY

1. No adverse events (AEs) will be expected during the course of study because there is no involvement of pharmacological drug or product. Both methods of membrane sweeping and transcervical Foley catheter do not contain drug or medication. Thus, the risk of uterine rupture is similar to spontaneous labour in women with previous Caesarean delivery. However, maternal discomfort and vaginal bleeding following membrane sweeping and unknown latex allergy following transcervical Foley catheter insertion may occur, and subjects will be informed of this risk in the informed consent.
2. All other invasive (amniotomy, fetal scalp sampling in the presence of non-reassuring fetal heart rate, instrumental delivery or emergency Caesarean section if indicated) and non-invasive procedures (maternal vital signs observation and intrapartum continuous fetal heart rate monitoring) and evaluations (abdominal and vaginal examination to assess labour progress) included in this protocol are considered to be standard of care in evaluation and management of women with one previous Caesarean delivery undergoing IOL and would have been performed as part of routine practice.

3. Report of adverse events eg. SAEs, SUSARs.
 - a. When adverse event of any type occurs, local SAE/SUSAR report will be created by principal investigator and notified via SAE Platform on NMRR website.
 - b. Subjects who experience SAE/SUSAR will be followed up by principal investigator and a follow up report will be submitted.
 - c. For “Non-life threatening SUSARs” eg. latex allergy associated with Foley catheter insertion, vasovagal attack following membrane sweeping, and cervical tear, initial report is to be submitted within 15 calendar days followed by a follow up report.
 - d. For “Life threatening SUSARs” eg. uterine rupture and maternal sepsis, initial report is to be submitted within 7 calendar days followed by a follow up report within the next 8 calendar days.

4. Process and duration of follow-up of adverse events
 - a. Latex allergy associated with Foley catheter insertion
 - i. Foley catheter will be removed immediately.
 - ii. Steroids and anti-histamine will be administered as rescue medication.
 - iii. Closed monitoring of vital signs and oxygen saturation for 24 hours.
 - b. Vasovagal attack following membrane sweeping

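### No visible eligibility criterion or form field screens for known latex allergy, although the Group 2 catheter is latex and the safety section foresees only unknown allergy

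*Combined protocol and SAP*

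**What the plan says.** **Who is eligible** (Selection and Withdrawal of Subjects, items 1 to 3). The source population is broad: "All pregnant women with one previous Caesarean section who are admitted to Sibug Hospital for IOL will be recruited in the study". The inclusion rule begins "The inclusion criteria are age at least 18 years old, gestational age ≥ 37 weeks, singleton pregnancy, reassuring fetal status" and ends with a ceiling on the modified Bishop score. Exclusion 3.a is "Women with ruptured membranes, intrauterine death, polyhydramnios, severe fetal anomalies, multiple pregnancy". Exclusion 3.b is "Women with contraindications for IOL eg. placenta previa, suspected macrosomia, suspected cephalopelvic disproportion, non-cephalic presentation, and obstructive pelvic masses".

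**What Group 2 receives** (Trial Design, 7.c.iii). "Foley catheter is an indwelling catheter made of latex rubber".

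**What the safety section expects** (Assessment of Safety, item 1). "unknown latex allergy following transcervical Foley catheter insertion may occur, and subjects will be informed of this risk in the informed consent". Item 3.c gives latex allergy linked to catheter insertion as an example of a non-life-threatening SUSAR. Item 4.a sets out what follows a reaction, starting with "Foley catheter will be removed immediately", then rescue medication and 24 hours of monitoring.

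**When allocation is fixed** (Trial Design, 5.c, 5.f and 5.h). Consent is taken at admission. The next envelope is opened once consent is signed, and induction follows the next morning.

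**What is recorded** (Trial Design, 7.a.i, and Appendix 3). Section A covers obstetric history, body size and the indication for induction. It has no allergy item.

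**The concern.** In a two-arm trial, every woman randomised should be able to receive either treatment. Here the exclusions address induction in general. No criterion addresses whether a woman is suitable for one of the two methods in particular.

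The word *unknown* in the safety section makes best sense if women with a known allergy have already been kept out, and nothing in the visible text keeps them out. The first thing at stake is safety: the criteria permit an exposure that the safety section appears to assume will not happen knowingly. The second is conduct. If the allergy came to light after the envelope was opened, only a woman allocated to the catheter would be unable to have her allocated treatment, and the protocol does not say what should then happen to her in the trial.

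**Working it through.** The plan states no figure on this point, so there is nothing to reproduce. The check is mainly a reading of the text, followed by a simple calculation of scale.

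**Step 1. Does any criterion cover known latex allergy?**

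- Inclusion criteria: age, gestation, singleton pregnancy, fetal status and Bishop score. No.
- Exclusion 3.a: a closed list of five conditions. No.
- Exclusion 3.b: an open list, but of contraindications to induction. Its examples concern induction or vaginal birth by any method. Latex allergy concerns one device, and a woman who has it could still be induced by sweeping. Not covered on the wording.
- Withdrawal criteria (Subject withdrawal, 6.a): voluntary withdrawal, enrolment outside the criteria, and spontaneous labour before the procedure. Allergy is not listed. A woman with known allergy would not count as wrongly enrolled, because she meets the criteria.
- Data collection form: no allergy field.

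In the visible text, latex appears only in the device description and in the safety section.

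**Step 2. Is there any other check before allocation?** One. Women are told of the risk at consent, and consent comes before the envelope. A woman who knows of her allergy could speak up or decline. No step requires staff to ask.

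**Step 3. What happens if the allergy is recognised after allocation?** The route is undefined. Assessment of Safety 4.a has the catheter removed after a reaction but does not withdraw the woman, whereas 4.b does withdraw a woman who has a vasovagal attack. If she withdrew at her own request, Subject withdrawal 6.b and 6.c would have her data destroyed and a replacement recruited.

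**Step 4. How often might it arise?** Inputs:

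- *p*, the proportion of randomised women with known latex allergy. Not in the documents; assumed 0.1% to 1%. This supposes that none is identified or declines at consent.
- *N*, the number randomised. The protocol gives only the first stage, 24 (12 per group). The final number is to be calculated after the interim analysis, so 64 and 200 are assumptions.
- Allocation is 1:1, so the Foley arm has *N*/2 women.

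Expected number in the Foley arm = *p* × *N*/2. Chance of at least one = 1 − (1 − *p*)^(*N*/2).

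| *N* | Foley arm | Expected, *p* = 0.1% | Expected, *p* = 1% | At least one, *p* = 0.1% | At least one, *p* = 1% |
|---|---|---|---|---|---|
| 24 | 12 | 0.012 | 0.12 | 1 − 0.999^12 = 1.2% | 1 − 0.99^12 = 11.4% |
| 64 | 32 | 0.032 | 0.32 | 1 − 0.999^32 = 3.1% | 1 − 0.99^32 = 27.5% |
| 200 | 100 | 0.10 | 1.0 | 1 − 0.999^100 = 9.5% | 1 − 0.99^100 = 63.4% |

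These are chances that such a woman is allocated to the catheter. They are not chances of a reaction.

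**The case against.** **Consent is a real safeguard.** The risk is disclosed before randomisation, and induction waits until the next morning, which leaves time for the allergy to be recognised. This stands in part. A reader might infer from the criteria that a woman with known allergy *will* be randomised. The documents support only that she *could* be. Disclosure is still not an eligibility check, and recognition overnight would come after allocation.

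**Part of the material cannot be seen.** The consent form (Appendix 2) and the flow chart (Appendix 1) are not available, and either could contain an allergy question. This stands, and it limits the claim to the visible protocol text. A question there would still not be a criterion in the protocol's eligibility section.

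**The inference from one word is thin.** *Unknown* appears once; items 3.c and 4.a refer to latex allergy without it. That is fair: the screening premise is implied, not stated. Classing the reaction among SUSARs, which are unexpected by definition, fits the same premise.

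**The arms remain comparable.** A reader might infer that one-sided losses would make the arms no longer exchangeable. That would require latex allergy to be related to the induction to delivery interval, and nothing in the documents suggests it is. Losing a woman for a reason unrelated to outcome costs numbers but does not bias the comparison. This objection stands.

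**The open list in 3.b leaves discretion.** Some, but the category it opens is contraindications to induction, which does not extend to a bar on one device.

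**Conclusion.** The point holds as a gap between sections. The device description, the eligibility criteria and the safety section do not agree on whether a woman with known latex allergy may be randomised. Taken literally, she may be, and she could be allocated to the latex arm. The grounds for acting are patient safety and the principle that each randomised woman should be able to receive either arm.

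The scale is small. Under the assumed prevalence, the expected number in the Foley arm runs from 0.012 (24 randomised, 0.1%) to 1.0 (200 randomised, 1%). The 63.4% in the table is the extreme corner of two assumed ranges and should not be cited alone. Nor does each such allocation amount to harm: the allergy may be missed, so that she is exposed, or recognised, so that she does not receive her allocation. For any one woman these are alternatives. Any one-sided loss after randomisation would be very small, and bias in the primary outcome is not shown.

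Severity: minor. The conclusion rests on the visible text only; the figures rest on an assumed prevalence and, beyond the first 24 women, an assumed sample size.

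**What to change.** Reconcile Trial Design 7.c.iii, the exclusion criteria and Assessment of Safety item 1, so that eligibility matches the premise the safety section already uses:

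- list known latex allergy among the exclusions, to be checked before the envelope is opened;
- add a yes/no latex allergy item to Section A of the data collection form, so that the check is documented;
- confirm that the consent form and the flow chart agree with the revised criterion.

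The cost is one line in the criteria, one tick-box and a very small loss of eligible women. The analysis does not change.
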